Theoretical Framework. This study is guided by the Health Information Technology Usability Evaluation Model (Health-ITUEM), a technology acceptance theoretical framework that guides usability evaluations for assessing mHealth technologies.⁸⁹ This technology acceptance model was developed in response to the current gaps in the extant usability literature⁹⁰ and was validated by [name] et al. for use with mHealth technology and has been widely used (cited 89 times since 2013). The Health-ITUEM integrates multiple concepts of usability from the Technology Acceptance Model⁹¹ and the International Organization for Standardization standard 9241-11.⁹² Guided by this model, we will carefully and iteratively refine the mLab App to ensure that the content and approach are engaging and usable since the two underlying tenets of technology acceptance are usefulness and ease of use.⁹³

Our proposed study, based on our preliminary work, uses a careful iterative process guided by the Health-ITUEM to refine and test a mHealth intervention for improving outcomes for youth across the HIV care

continuum. The project will develop and test the mLab App, an innovative mobile and connected technology that combines HIV prevention information, with push notification reminders for testing, mobile phone imaging of a lateral flow diagnostic assay (OraQuick) and automated image processing to provide accessible, objective, secure, and real-time feedback on test results. The mLab App also contains an automated data collection and results reporting feature. The reporting feature relays test results back to the research team, triggering messages to encourage future repeat testing for a non-reactive test or for a reactive test, linkage to confirmatory testing and treatment. The proposed study is highly significant as summarized below:

- Mobile and connected point-of-care diagnostics are promising tools to increase the uptake of HIV self-testing with the goal to improve diagnosis of previously undiagnosed individuals and link youth to care.
- This project focuses on increasing HIV testing in one of the highest risk populations—Black and Latino YMSM and YTGW (18-29 years).
- The study is designed to answer the most important question that will drive this technology forward: Will the mLab App improve the uptake of the HIV self-test in previously undiagnosed youth?

Preliminary Data: We have conducted four preliminary studies to support the use of this intervention for youth.

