mLab Image-Processing Evaluation Methods. During use of the mLab App, participants will submit images of their Oraquick self-test to the app for analysis by an automated image-processing algorithm. Prior to submitting this image for analysis, participants will be asked to interpret the results of the test using the instructions that are provided standard with the OraQuick test. This self-reported result will be recorded and uploaded with the user-submitted image of their rapid test. Study team members with expertise in rapid test use and analysis will evaluate the uploaded images of each rapid test, and provide an additional assessment. The user-submitted result and the study team assessment will not be used by mLab in its automated image-processing. All users that submit tests that are identified as positive, either by the automated image-processing in mLab, the study team personnel's inspection of the image of the rapid test, or by the study participant themselves, will be referred for confirmatory testing.

(*Hypothesis 3*).**mLab Image-Processing Data Analysis Plan.** Including the confirmatory test, which will be treated as the gold standard to determine whether a test result is truly false or positive, there will be results from four analysis methods collected on the same set of tests (1. User-submitted results, 2. Study team interpretation of uploaded images, 3. Automated mLab App results, 4. Confirmatory testing). The sensitivity and specificity for each of these methods will be compared using McNemar's test. This will result in the following statistical comparisons for both sensitivity and specificity: 1) user-submitted analysis to study team analysis, 2) user-submitted analysis to mLab analysis, 3) study team analysis of uploaded images, 4) user-submitted analysis to confirmatory testing, 5) study team analysis to confirmatory testing, 6) mLab analysis to confirmatory testing.

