- 5) Window Period for Interpretation of Results: In the mLab App, we have added in 2 points of instruction related to the 20-40 minute window period for the Oraquick results – see Appendix L, slides 7 and 11. Second the images will be time stamped and we will not return algorithm results if the time from reporting in screen 7 and the time to take a picture in screen 11 has been less than 20 minutes or more than 40 minutes.
- 6) Invalid Test Results: If the participant reports an invalid result – the software will send the following message back to the study participant: You reported that your results are invalid. An Invalid test result means that there was a problem running the test, either related to the specimen or to the Test Device. An Invalid test will not be interpreted by the mLab App. Repeat the test with a new Divided Pouch and a new oral fluid. Please contact the study team if you are unable to get a valid test result upon repeat testing. If the participant reports an invalid test then we will turn off the ability for the mLab App to return the algorithm results to the participants. However, invalid images will still be stored in REDCap and reviewed by the study team.
- 7) Imaging Algorithm: The parameter values in the mLab App's image processing algorithm have been validated and selected to primarily optimize sensitivity and specificity. However, it is possible for the mLab App to return both false positives and false negatives. The study team will monitor the images that are sent using the mLab App, and will contact study participants in the event of either: 1) the mLab App returns an incorrect result, and 2) a discrepancy between the participant's manually reported result and the mLab App result.

c. Additional Planned Procedures for Protecting Against/Minimizing Potential Risk/Additional Protections for Children

Procedures in the Event of a Reactive HIV Test

In the event a participant has a reactive HIV test, study team members will counsel the participant regarding the meaning of his result. Specifically, the study team will reiterate with the participant that:

- 1) His result is a preliminary positive and it is likely that he is infected with HIV;
- 2) The preliminary positive result needs to be verified with confirmatory testing;
- 3) He needs to return for the results of his confirmatory testing; and
- 4) Resources for counseling and referral to care are available to him.

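### The plan does not mask study-team image readers to the participant's and the app's results, so their read may not be independent

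*Combined protocol and SAP*

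**What the plan says.** Under Aim 2, mLab Image-Processing Evaluation Methods, participants interpret their own test before sending the picture. The plan adds: "This self-reported result will be recorded and uploaded with the user-submitted image of their rapid test". Study-team members with rapid-test expertise then "will evaluate the uploaded images of each rapid test, and provide an additional assessment". One independence rule follows: "The user-submitted result and the study team assessment will not be used by mLab in its automated image-processing".

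The mLab Image-Processing Data Analysis Plan takes the confirmatory test as gold standard. On the four methods it says "The sensitivity and specificity for each of these methods will be compared using" McNemar's test, and it lists six comparisons. The first is "1) user-submitted analysis to study team analysis", the fifth sets the study team against confirmatory testing, and the third names the study-team read with no comparator.

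Under Protections against Risks, item 7 (Imaging Algorithm): "The study team will monitor the images that are sent using the mLab App". Participants are contacted if the app is wrong, or if there is "a discrepancy between the participant's manually reported result and the mLab App result". Item 6 has the study team review images that participants reported as invalid. The Theoretical Framework section adds: "The reporting feature relays test results back to the research team".

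**The concern.** A comparison of readers is informative only if each reads without knowing the others' calls. The Background and the preliminary studies describe weak or fuzzy lines as the problem the app addresses, and those are the reads most easily swayed by someone else's answer.

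Here the participant's answer travels with the picture, and the team that reads the picture also holds the app's answer for monitoring. If a reader sees either before deciding, errors by the participant or the app can carry over into the expert read. McNemar's test uses only discordant pairs, so borrowed calls remove the information it needs. The comparison would then misstate how participants, and probably the app, measure up against an expert eye.

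**Working it through.** The plan gives no reader accuracy, agreement rate, sample size or power for these comparisons, so there is no stated figure to reproduce. The main check is textual; the arithmetic shows direction and possible size on assumed values.

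**1. What is protected from what**

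| Reading | Independence stated in the plan |
|---|---|
| App | Yes: does not use the participant's or the team's read |
| Participant | Yes, by order: entered before the image is submitted |
| Study team | None: no masking, no order, no separation of readers from monitoring staff |

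The study-team read is the only one of the three image-based reads with no stated safeguard.

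**2. How many comparisons use it**

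Four methods give 4 × 3 / 2 = 6 pairs. Five are fully named; the missing pair is study team versus mLab, so comparison 3 is presumably that one (an inference). The read then enters comparisons 1, 3 and 5: 3 of 6, or 6 of 12 tests, counting sensitivity and specificity separately.

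**3. Direction**

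Let s_u be the participant's accuracy and s_r the accuracy of a masked reader, with errors independent given true status. Let a be the share of would-be disagreements in which the reader adopts the participant's call. All are assumptions.

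- Discordant cells: s_r(1 − s_u)(1 − a) and s_u(1 − s_r)(1 − a).
- Observed difference: (1 − a)(s_r − s_u).
- Reader accuracy: s_r − a(s_r − s_u).

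Both cells shrink by (1 − a), so comparison 1 moves toward agreement. For example, 20 masked discordances, a number not taken from the plan, would become 15 at a = 0.25 and 10 at a = 0.50.

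**4. Sensitivity, assuming s_u = 0.90 and s_r = 0.97**

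Masked cells: 0.97 × 0.10 = 0.097 and 0.90 × 0.03 = 0.027, total 0.124. Power is for the exact two-sided McNemar test at 0.05.

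| a | Difference | Discordant | Reader's gap to gold standard | Power, 25 positives | Power, 40 positives |
|---|---|---|---|---|---|
| 0 | 0.070 | 12.4% | 0.030 | 1.7% | 8.2% |
| 0.25 | 0.0525 | 9.3% | 0.0475 | 0.5% | 3.5% |
| 0.50 | 0.035 | 6.2% | 0.065 | 0.1% | 0.8% |

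The 25 to 40 positives are the plan's figure from its Hypothesis 2 text, which compares two arms. Only arm 1 submits images, so fewer positives would be available here.

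In comparison 5 the gap widens, because the reader borrows from a less accurate source. Swap the two values (reader 0.90, source 0.97) and at a = 0.50 reader accuracy is 0.90 + 0.50 × 0.07 = 0.935. The gap then narrows from 0.10 to 0.065. Comparison 5 can go either way.

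**5. Specificity, assuming s_u = 0.97 and s_r = 0.99**

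Masked cells: 0.99 × 0.03 = 0.0297 and 0.97 × 0.01 = 0.0097, total 0.0394.

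| a | Discordant | Power, 400 negatives | Power, 800 negatives |
|---|---|---|---|
| 0 | 3.94% | 44% | 78% |
| 0.25 | 2.96% | 31% | 64% |
| 0.50 | 1.97% | 17% | 44% |
| 0.75 | 0.99% | 4% | 17% |

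Arm 1 receives at most 210 × 4 = 840 kits, so 800 is near the ceiling.

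**6. Route to Hypothesis 3**

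Its two parts are mLab versus confirmatory testing (comparison 6) and mLab versus participant (comparison 2). Neither uses the study-team read. A positive call by app, participant or team triggers referral for confirmatory testing, so a reader who borrows a positive adds no referral. What remains is a test that both participant and app call negative: there the team read is the only one of the three triggers left, and an influenced reader might not pull it.

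A true positive lost this way is a discordant pair removed from comparison 6. In comparison 2 it is concordant, so McNemar's statistic is unchanged, although both sensitivity estimates rise. If the app's only miss were lost, its observed sensitivity would go from 24/25 = 96% to 24/24 = 100%, or from 39/40 = 97.5% to 39/39 = 100%.

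**The case against.** The strongest reply is that the plan never says a reader sees the other results. Uploading a result with an image describes data transfer, not what appears on the reader's screen. The readers' stated task is to evaluate images. They are described as having rapid-test expertise, whereas monitoring falls to the study team generally, and nothing says these are the same people. Judging that the app was wrong may even require the team to read first. Reading procedures could also sit in the workflow attachment, Figure 1, Appendix L or pages missing from the available text. All of this stands: exposure is a possibility that the plan leaves open, not a documented fact.

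A reader might also infer that all three study-team comparisons are biased toward agreement. The documents do not support that: comparison 5 can move either way, and comparison 3 is incomplete as written.

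Nor would masking rescue the sensitivity comparison. On the assumed accuracies, its power is at most 8.2% even with fully masked reads.

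What survives is the asymmetry. The plan safeguards the algorithm's independence and says nothing of the reader's, just where the participant's answer is bundled with the image.

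**Conclusion.** The concern holds as a gap in the plan: masking of the study-team reader is not stated, so independence of that read is not assured. Comparison 1, and comparison 3 if its comparator is mLab, may be pulled toward agreement; comparison 5 may be biased in either direction. How much depends on the share of borrowed calls, which is unknown; the accuracies, numbers of negative tests and shares used above are illustrative.

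It would be tempting to conclude that Hypothesis 3 or the trial's main result is compromised. That does not follow. The primary outcome is self-reported testing, the gold standard is the confirmatory test, and comparisons 2 and 6 do not use this read. The only indirect route is a test called negative by both participant and app. Even there a confirmatory result may still be obtained, since the protocol recommends confirmatory testing for negative results too and refers negatives on request.

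This is a modest weakness in a secondary evaluation, worth correcting because prevention is cheap and later repair means re-reading images.

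**What to change.** In mLab Image-Processing Evaluation Methods, state that:

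- the study-team reader is shown only the image;
- the read is recorded and locked before the participant's and the app's results are opened for the item 7 check and any contact or referral;
- only the locked read enters the comparisons that involve the study team.

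In the Data Analysis Plan, complete comparison 3 by naming its comparator (by elimination, mLab).

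The cost is a small change to the order of data entry and a short addition to the protocol. It needs the same staff and the same single read, and leaves the monitoring and referral rules as they are. If monitoring cannot wait for the expert read, use readers separate from the monitoring staff. If the attachments already specify masking, a cross-reference is enough. If images have already been read unmasked, a masked re-read of the stored images would be needed for these comparisons.

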
Aim 1: Refine the user interface of the mLab App – a mobile and connected health intervention for increasing the uptake of rapid home HIV self-testing (OraQuick) and linkage to care – by employing rapid cycle iterative design methods with feedback from human computer interaction experts (N=5), end-users (N=20), and youth advisory board members (N=10).

Aim 2: Evaluate the efficacy of the mLab App in improving both HIV testing rates and linkage to care versus standard preventive care in 525 Black, Latino and other young men and transgender women (inclusive of YMSM and YTGW age 18-29 years) in a 12-month multi-site trial, with randomization to three groups (intervention, standard of care-HIV information control arm, HIV home tests) at each site.

Hypothesis 1. Youth randomized to the mLab App arm (arm 1), as compared to youth in the standard of care HIV information control arm, will have: a) increased rates of HIV testing within the first 6 months of the trial; and b) increased rates of re-testing in months 7-12 of the trial.

Hypothesis 2. The total number of youth who test HIV positive and link to care in the **mLab App** arm will be greater as compared to the standard of care HIV information control arm.

Hypothesis 3. The image processing in the **mLab App** will: 1) have no statistically significant difference in sensitivity or specificity when compared to confirmatory testing, 2) have greater sensitivity and specificity when compared to the user-submitted self-analyses.

Aim 3: Monitor and analyze paradata to understand the effect of user engagement of the **mLab App** on improving HIV testing rates and linkage to care.

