Missing Data. Multiple imputation (MI) methods will be applied to address missing values under the missing at random (MAR) assumption (i.e., missingness can be fully accounted for by variables with complete information).¹⁴¹ These analyses will be complemented with assessment of how sensitive the inferences are to the MAR assumptions. Sensitivity analysis will be performed based on selection models for dropout.¹⁴²⁻¹⁴⁴ Intention-to-Treat (ITT) Analysis: All analyses will use the ITT principle,¹⁴⁵ which requires subjects' data to be analyzed as randomized, regardless of whether they used the mLab App or not.

Aim 3: Monitor and analyze paradata to understand the effect of user engagement of the mLab App on improving HIV testing rates and linkage to care.

To understand barriers and/or facilitators of its use, the mLab app will automatically collect paradata for each user interaction throughout the study. This paradata is considered "free" in that it does not require any additional effort from the user.¹⁴⁶ This data will be analyzed for each user, as well as aggregated to understand what component of the intervention lead to behavior change. We will specifically examine who uses the mLab App and how frequently it is used over time.

Methods. We will capitalize on the use of the extant mLab software which is written as a mobile-friendly web application in hypertext markup language (HTML), hypertext preprocessor (PHP), JavaScript, and Python (for computer vision), and integrates with REDCap for backend data storage. On each page of the mLab app, a PHP script logs every user interaction before the page of the application is displayed to the user. Therefore, any event that would refresh or send the user to a new page (e.g., HTML links) initiates an event-driven paradata capture. The PHP script transmits the data to REDCap through the secure REDCap API.

Data Analysis. The primary paradata that will be collected is shown in Table 4. From this data, we will derive the following use data for each session: duration on each page, page progression through the application, time from login to result, number of rapid test pictures previewed before sent for result, and total time prior to logout. We will analyze the data on multiple scales and perspectives: individual-level (i.e. user-level), application-level, page-level, session-level, and how these differ by demographic characteristics, HIV testing history, technology

Table. Paradata Collected for Each mLab Event

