This study will be submitted to the IRB before starting the study. We will be careful to ensure that no coercion occurs during the recruitment periods by ensuring the voluntary participation of both healthcare providers and patients. All participants will be screened to assess for study eligibility. Non-participation will not affect patients' medical care in any way.

- 1) Confidentiality: The smartphone that is connected to the mLab App will require a password. All study data, including mLab App results will be encrypted and stored on secure HIPAA-compliant servers at the Columbia University Medical Center campus. All study data will be kept in password-protected computers or file cabinets in locked offices. All study data will be maintained in a completely secure and HIPAA-compliant environment. All servers have HIPAA-compliant security. Nonetheless, there is always the risk of a data breach, so we will make our study participants aware of this risk upon enrollment.
- 2) False Negative Results: The mLab App has the potential for providing a false negative result, especially during the period of acute HIV infection in which a newly infected individual may be most contagious.

We will clarify these issues before giving the mLab App to participants, test their understanding of the limitations of the HIV Home Test with a structured instrument (Appendix B), provide a study information card that contains information about test limitations, and recommend use of condoms regardless of the test outcome. Upon enrollment, we will explain to participants that the mLab App cannot determine their status with 100% accuracy. The mLab App may not detect acute HIV infection.

- 3) Risk of receiving a false positive HIV home test result: Participants will be informed of the limitations of the mLab App, including the occurrence of false positive results. Again, the study team will stress the need for confirmatory testing.
- 4) Distress a participant may experience if s/he receives a positive HIV result at home: If a research subject gets a positive result in the mLab App at any point during participation in this study, this result will require confirmation. The study team will provide the participant with a confirmatory test and referrals for treatment and care if needed, including psychological assistance.

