This study has not been designed for the direct benefit of its participants; however, there are a number of ways in which they may derive benefit. The proposed research will inform the delivery of HIV prevention messages. The knowledge gained will contribute to the body of knowledge regarding the use of health information technology for improving the lives of MSM at risk for HIV. The avoidance of HIV through study participation will be a significant personal benefit to participants.

Participants in the mLab App arm will be referred to standard-of-care services either at the time of a reactive HIV test result (if sero-positive) or the end of the study (if sero-negative). Standard-of-care services for HIV-negative MSM, regardless of risk level, includes provision of HIV/STI testing (based on the local HIV testing standard procedure) as described below. Standard-of-care services for HIV-positive MSM include provision of linkage to HIV care services based on the standard-of-care services offered in the local project site community.

Importance of the Knowledge to be Gained

Each new case of HIV constitutes a burden to the individual, the health care system of our country, and to society at large. Our study is expected to result in benefits for society since it will provide a knowledge base for HIV and STI prevention strategies. Point-of-care tests are used worldwide to screen individuals for antibodies against HIV. The risks to research participants enumerated above are reasonable in relation to the anticipated increase in knowledge on the potential use of self-testing and behavioral economics for improving outcomes across the HIV care continuum.

ALTERNATIVES:

The alternative is not to participate in the research.

DATA SAFETY MONITORING PLAN:

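### Strips that all three readers call negative get no routine confirmatory test, so sensitivity for HIV infection cannot be estimated as Hypothesis 3 plans, and the analysis set is undefined

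*Combined protocol and SAP*

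**What the plan says.** The mLab Image-Processing Data Analysis Plan (Aim 2) makes the confirmatory test the gold standard and states that "there will be results from four analysis methods collected on the same set of tests": user, study team, app and confirmatory test. Sensitivity and specificity are then compared pairwise by McNemar's test. The third listed comparison names only the study-team read and no comparator. Hypothesis 3 Part 1 expects the app to "have no statistically significant difference in sensitivity or specificity when compared to confirmatory testing"; Part 2 expects the app to do better than the user.

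On who gets the reference test, the Evaluation Methods paragraph refers "All users that submit tests that are identified as positive, either by the automated image-processing in mLab", by the study team's inspection of the image, or by the participant. Item 4 under Risks Specific to the Use of OraQuick, and item 3 of the intervention-arm risk list, offer further testing to negatives only when they ask. The Follow-Up Surveys paragraph describes no study HIV test at 6 or 12 months.

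Other places read differently. Arm 1-Intervention Arm and Recruitment and Informed Consent advise confirmation after negative as well as positive results. Item 4 of the intervention-arm list makes additional testing available to everyone. Potential Benefits refers sero-negative app users to services, including testing, at study end.

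On images, "Study team members with expertise in rapid test use and analysis will evaluate the uploaded images of each rapid test". On missing data, "Multiple imputation (MI) methods will be applied to address missing values under the missing at random (MAR) assumption", followed by a promise to assess sensitivity to that assumption and the sentence "Sensitivity analysis will be performed based on selection models for dropout".

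**The concern.** The four-method data set cannot exist as described for strips that no reader called positive. The protocol expects some of these to come from infected users. Item 2 under Risks Specific to the Use of OraQuick says infections acquired in the previous three months may be missed, and Protections against Risks says "The mLab App has the potential for providing a false negative result, especially during the period of acute HIV infection". With reminders at 3, 6, 9 and 12 months, strips from that window are likely.

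Such strips leave the sensitivity denominator, so the trial could report a figure for detecting infection that mostly reflects line reading. The plan also does not say whether unverified strips are dropped, counted as uninfected or imputed. For specificity that choice matters a great deal. Finally, losing app misses pushes the sensitivity half of Part 1 towards the result it hopes for.

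**Working it through.** The plan gives no sample size, precision or expected accuracy for Hypothesis 3, so there is no figure to reproduce. **All error rates below are assumptions**, and strips are treated as independent.

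**1. Sensitivity.** Let S be the share of infected strips that show a line. App, user and team miss 5%, 10% and 2% of visible lines.
- True app sensitivity = 0.95 S.
- Independent readers: q = 1 - S[1 - (0.05)(0.10)(0.02)]; observed = 0.95 S/(1 - q) = 95.0%.
- Maximum dependence (every line the team misses is also missed by app and user): q = 1 - 0.98 S; observed = 0.95/0.98 = 96.9%.

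| S | true app sensitivity | q, independent | excess, independent | excess, maximum dependence |
|---|---|---|---|---|
| 0.85 | 80.8% | 0.150 | 14.3 points | 16.2 points |
| 0.92 | 87.4% | 0.080 | 7.6 | 9.5 |
| 0.95 | 90.3% | 0.050 | 4.8 | 6.7 |
| 0.99 | 94.1% | 0.010 | 1.0 | 2.9 |

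The app reads 95% of visible lines, so reading misses explain only 95.0 - 95 = 0.0 to 96.9 - 95 = 1.9 points. The rest is assay misses.

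If 20% of all-negative strips were verified at S = 0.85, observed = 0.8075/(0.850 + 0.2 x 0.150) = 91.8%, and the excess falls from 14.3 to 11.0 points.

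**2. Infected strips in arm 1.** The Aim 2 Data Analysis section expects 25-40 positives. A pro-rata share (210/525) is 10-16, taken here as users. Suppose infections fall evenly over four quarters, with a strip each quarter. Four infected users then give 4+3+2+1 = 10 infected strips, or 4+3 = 7 if each stops after the first strip beyond the window. That makes 25-40 strips (x 10/4) or about 17-28 (x 7/4). In-window strips are 4/10 or 4/7 of these, so S = 0.85 means 37.5% or 26% of in-window strips show no line; S = 0.99 means 2.5% or 1.8%.

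**3. Part 1, sensitivity half.** The confirmatory test is the reference, so discordance runs one way and exact two-sided McNemar p = 2 x 0.5^b for b app misses: b = 5 gives 0.0625, b = 6 gives 0.031. At least 6 misses are needed. Counted misses are Bin(n, 1 - 0.95 S) with full verification and Bin(n, S x 0.05 x [1 - (0.10)(0.02)]) under referral.

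| S | P(at least 6), full verification, n = 17 / 25 / 28 / 40 | referral, n = 40 |
|---|---|---|
| 0.85 | 9% / 35% / 46% / 81% | 0.6% |
| 0.92 | 1.4% / 9% / 13% / 39% | 0.9% |
| 0.99 | 0.03% / 0.3% / 0.5% / 3.0% | 1.3% |

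If 10-16 is instead the number of infected strips, full verification at S = 0.85 gives 0.5% to 7.0%.

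**4. Specificity.** Assume false-positive rates of 2% (app), 1% (user) and 0.5% (team), independent. The share of uninfected strips verified is 1 - (0.98)(0.99)(0.995) = 3.5%. App specificity on verified strips only is 1 - 0.02/0.0347 = 42%, whatever the number of strips. With a 1% app rate it is 1 - 0.01/0.0248 = 60% against a true 99%.

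Counting all-negative strips as negatives: of at most 4 x 210 = 840 strips, take 40 as infected, with 40 x 0.15 = 6 missed by all. Then (800 x 0.98 + 6)/(800 + 6) = 98.0%. The missed infections barely matter.

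**5. Tests that survive.** Every strip on which app and user disagree has a positive read and is referred. All-negative strips are concordant and do not enter McNemar. The app-versus-user test (Part 2) is therefore not biased if every referred user is tested. App false positives also trigger referral, so the specificity half of Part 1 loses none of them.

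**The case against.** Several passages advise or offer testing after a negative result, and imputation is planned. These are advice, availability or an end-of-study referral; none schedules a test or ties a result to a strip. They would shrink the bias, as the 20% case shows, but not remove it while negatives are verified less often than positives.

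A reader might infer that multiple imputation fails because verification depends on the reads. That is not a breach of MAR, since the reads are recorded. The obstacle is that the all-negative cell would hold few verified strips, from people who chose testing, so imputing there is extrapolation. The promised check on MAR is general; the only method named concerns dropout.

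A reader might also infer that sensitivity can only be overstated. The documents do not support that: users, not strips, are referred, and no linking rule is given. If a later positive result were applied to a user's earlier strips, pre-infection strips would count as misses and sensitivity could be understated. Nor is some bias certain: at S = 0.99 the chance that no infected strip is assay-negative is 0.99^17 = 84% to 0.99^40 = 67%. The documents name no confirmatory assay; if it shared the window, even full verification would not show these misses.

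Finally, the app is meant to read lines, and reading misses add little. That stands, and it is the reason to change the target of the analysis.

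**Conclusion.** The concern holds in a conditional form. With results tied to the triggering strip, and a confirmatory test that detects the missed infections, sensitivity for infection is overstated by about 1/(1-q) for every reader. The bias is nil if q = 0 and smaller if some negatives are verified. Its existence rests on the protocol's own statements; its size (1.0 to 16.2 points for the app) rests on assumed rates.

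A reader might suppose that Part 1 would be non-significant even with full verification, so that nothing is lost. That holds only if the expected positives are counted as strips or S is high. With 17-40 infected strips and S = 0.85, the chance of a significant result is 9% to 81% with full verification and below 1% under referral. The pro-rata split is itself an assumption, since arm 1 is expected to test more.

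Specificity is recoverable with a stated rule, and the app-versus-user comparison stands. App performance is a secondary goal and Hypothesis 1 is unaffected. The analysis should still be changed, because as written it reports a sensitivity that the design cannot estimate.

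**What to change.** In the mLab Image-Processing Data Analysis Plan:

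1. Make the main app-performance analysis the positive and negative percent agreement of the app, and of the user, with the study-team read on all uploaded images. For the analysis record, enter the team read before the app and user results are opened, leaving the safety review in Protections against Risks (item 7) as it is. Report separately the images taken outside the 20-40 minute window or reported invalid.
2. State that sensitivity for HIV infection is not estimable under this verification scheme, and do not treat non-significance in the sensitivity half of Part 1 as support.
3. Compute specificity with all-negative strips counted as negatives, and state that assumption. Keep the app-versus-user McNemar among strips with a confirmatory result. State that a confirmatory result applies to the strip that triggered referral.
4. Reconcile the statements on testing after a negative result: Arm 1-Intervention Arm, Recruitment and Informed Consent, item 4 of the intervention-arm list and Potential Benefits on one side; the Evaluation Methods paragraph, OraQuick risk item 4 and item 3 of the intervention-arm list on the other.

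Cost: rewritten text and a small workflow step for the order of reads; no added tests, since the team already reads every image. The claim narrows from detecting infection to reading the strip correctly. Image faults shared by team and app may raise agreement. Positive agreement stays imprecise: 15/16 has an exact 95% interval of 70% to 99.8%.
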